8.2.4 Blinded Review / Final Statistical Analysis Plan

The Sponsor will convene a Blinded Data Review after the data have been cleaned, but before the study is unblinded (i.e., interim analysis). The review will be performed within the framework of the requirements of ICH E9.

The terms of reference of the Blinded Data Review shall include, but not be limited to:

- the determination of whether protocol violations are 'major' or 'minor'
- the allocation of patients to analysis sets
- a review of missing data and outliers, their assessment and definition of handling
- a review of the distribution of the efficacy variables, considering any implications for the proposed methods for statistical analysis
- a review of whether additional covariates need to be included in the analyses
- the finalization of the SAP

The Blinded Data Review Report will include the definition of major and minor protocol deviations and the final allocation of patients to analysis sets.

The Blinded Data Review Report will be finalized before the blind will be broken. Formal records shall be kept of when the statistical analysis plan was finalized as well as when the blind was subsequently broken.

8.2.5 Definition of Populations

Safety population

The safety analysis set will consist of all randomised patients who received at least one dose of study medication.

Clinical Study Protocol SMOF-018-CP3 Smoflipid 20% lipid injectable emulsion

Intention-to treat (ITT) population

The primary confirmatory analysis of superiority will be performed using the ITT population. The ITT analysis set will consist of all randomised patients.

Per protocol (PP) population (main analysis) set

The primary analysis of non-inferiority will be performed using the PP population. The PP analysis set includes all patients who receive study drug for at least 14 days without major protocol violations. Major protocol deviations are those that may significantly impact the completeness, accuracy, and/or reliability of the study data. A patient may be excluded from the PP analysis set for, but not limited to, any of the following conditions:

- Patient does not meet critical inclusion/exclusion criteria
- Patient is removed from the study prior to day 28 for other reasons than elevated conjugated bilirubin levels
- Incorrect administration of study product

A blinded review will be performed before breaking of the blind in order to assess and define the handling of missing data, data issues as well as to classify major and minor protocol violations. The final allocation of patients to analysis sets will be performed during the blinded review as described in Section 8.2.4.

8.2.6 Interim and Final Analysis

A two-stage adaptive group-sequential procedure will be performed, using a global significance level of $\alpha=0.025$. After 100 patients in total (50 in each arm) have completed the study per protocol an interim analysis will be performed. For the interim analysis, the following limits for a premature termination of the trial will be defined (Bauer, et al. 1994):

$\alpha_0 = 0.5$	lower limit for the premature termination of the trial with negative result
$\alpha_1 = 0.0102$	upper limit for the premature termination of the trial with rejection of the null-hypothesis

According to the one-sided formulation of the alternative hypotheses all p-values and confidence intervals in the following sections must be calculated one-sided.

At the interim analysis the primary efficacy criterion will be assessed as described in Section 8.2.3 at the significance level α_1 . The null-hypothesis H_{10} can be rejected if the upper limit of the $(1-\alpha_1)\cdot100\%$ CI is less than 1.2 (related to the NI hypothesis), H_{20} can be rejected if the corresponding p-value p_1 is less than α_1 (hypothesis of superiority). In this case the study may be terminated early due to efficacy.

If the upper bound of an $(1-\alpha^*)\cdot100\%$ CI is less than 1.2 only for $\alpha^* \geq \alpha_0$ the null hypotheses will be considered accepted which allows early termination due to lack of efficacy.

Clinical Study Protocol SMOF-018-CP3 **Smoflipid 20% lipid injectable emulsion**

If non-inferiority cannot be shown at the time of the interim analysis, but the upper-bound of the $(1 - \alpha^*) \cdot 100\%$ CI is less than 1.2 for any α^* with $\alpha_1 < \alpha^* < \alpha_0$ (non-inferiority hypothesis) then the second part of the trial will be planned with an adaptation of the sample size. The results of the interim analysis at stage 1 influence the second stage as follows:

Let $p_1 = \min(\alpha^* | \text{upper bound of } (1 - \alpha^*) \cdot 100\% \text{-CI} < 1.2)$ the actual level of significance for non-inferiority at stage 1. In order not to exceed the global significance level $\alpha = 0.025$, the corresponding level of significance in the second stage p_2 needs to satisfy $p_1 * p_2 \leq 0.0038$. Thus, the required number of patients can be calculated for the significance level $p_2 = 0.0038/p_1$ (i.e., non-inferiority of Smoflipid compared to Intralipid is shown if the upper limit of the $(1 - p_2) \cdot 100\%$ CI is < 1.2 at the second stage).

To determine the sample size necessary to prove superiority of Smoflipid compared to Intralipid after non-inferiority is shown at the second stage of the study, the p-value p_1' of the actual difference between Smoflipid and Intralipid at the first stage will be calculated. It determines the level of significance $p_2' = 0.0038/p_1'$ at which H_{20} must be tested after H_{10} is rejected at the second stage in order not to exceed the global one-sided significance level $\alpha = 0.025$.

If H_{10} can be rejected at the significance level α_1 but $\alpha_1 < p_1' < \alpha_0$ with p_1' the p-value of the actual difference between Smoflipid and Intralipid at the first stage, then the second part of the trial will be planned with an adaptation of the sample size in order to enable rejection of the null hypothesis H_{20} (superiority). Similar to the explanation in the preceding section, the required number of patients can be calculated for the significance level $p_2' = 0.0038/p_1'$.

Additionally, the risk ratio between Smoflipid and Intralipid with respect to the primary outcome parameter observed in the first part of the trial will be taken as a basis for the relevant difference when adapting sample size for the second part of the study.

The conditional power for planning stage 2 should be at least 80%.

If the resulting sample size for the second part of the study with respect to the non-inferiority hypothesis is greater than the prognostic recruiting rate the study will be terminated after the first part of the study. Based on current estimates a maximum study size of 200 patients per group may be feasible for the scheduled recruitment period. In this case all data will be analysed descriptively and in an exploratory way. Confirmatory hypothesis testing will be dropped because the respective statistical tests will suffer from a serious lack of power and cannot provide appropriate results for reliable decisions on the study hypotheses.

To assure the stochastic independence of the two p-values, both trial parts must be analysed separately. This procedure ensures a global significance level of $\alpha = 2.5\%$.

In accordance with ICH E9, the execution of the interim analysis must be a completely confidential process. All staff involved in the conduct of the trial - except for those who are directly involved in the execution of the interim analysis - will remain blinded to the results of the analysis. Investigators will only be informed about the decision to discontinue the trial if

Clinical Study Protocol SMOF-018-CP3 **Smoflipid 20% lipid injectable emulsion**

the trial will be terminated prematurely based on the result of the interim analysis. A second statistician, other than the trial statistician, and who is independent from the study will conduct the interim analysis. Further details will be provided in the interim analysis plan and/or Data Safety Monitoring Board (DSMB) charter.

After the interim analysis, the Statistical Report will be forwarded to an independent DSMB (refer to Section 13.5).

8.2.7 Analysis of Secondary Outcome Measures

Exploratory analysis of the secondary outcome measures for efficacy and safety as described in Section 8.2.1 will be performed comparing both treatment groups:

Summary tables will be presented. Between groups comparisons will be performed with adequate statistical tests (e.g. repeated measurement analyses examining the course of variables over time, the Kaplan-Meier method for time to event measures, Wilcoxon tests for continuous and Fisher's exact tests for binary outcome measures). The corresponding effect size measures and confidence intervals will be presented in addition.

If the study is stopped prematurely after the interim analysis because the required sample size to demonstrate superiority or non-inferiority for the primary outcome measure is too large to be feasible, the analyses of secondary outcome measures will be performed only with descriptive statistics and the statistical tests planned above will be dropped.

(In some cases, model-based analyses (such as competitive risk analysis) might be used to examine differences between treatment groups since they provide helpful parameters to describe treatment effects. Respective results will only be interpreted in an exploratory and descriptive manner. Details will be planned in the SAP for the final analyses.)

Adverse events (AEs) will be categorized by primary system organ class. The number, intensity, relation to study medication and action taken will be described by frequency tables. Serious adverse events will be discussed separately.

The analysis of the secondary efficacy outcome parameters will be performed using the ITT population (intention-to-treat) and the per protocol population (per protocol) in the sense of sensitivity analyses.

The analysis of the secondary safety outcome parameters will be performed using the safety population.

A comprehensive SAP covering the details of all methods used to analyze the various parameters will be prepared before unblinding. The SAP will be reviewed, and if needed, updated before unblinding.

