5.2 Rationale and Purpose of the Study

Fresenius Kabi, the manufacturer of Smoflipid, has applied for approval of Smoflipid in the United States (US). In order to meet the request of the Food and Drug Administration (FDA), a post-marketing study will be performed in hospitalized neonates and infants to show safety superiority of Smoflipid compared with Intralipid, a currently approved lipid emulsion in the US.

The present protocol describes a randomized, controlled, double-blind study in which either Smoflipid or Intralipid will be administered as part of a well-defined PN regimen to hospitalized preterm and term neonates and infants requiring at least 28 days of PN. The purpose of this study is to demonstrate the superiority in safety of Smoflipid (investigational drug) compared with Intralipid (reference drug) by evaluating the effect of these products on conjugated serum bilirubin levels. In addition, the study will explore if Smoflipid safely provides sufficient energy and essential fatty acids (EFAs) to ensure appropriate growth and development in these pediatric patients.

Sterols (including phytosterols) and α -tocopherol in the blood of the study patients will be evaluated to assess whether a correlation exists between the sterol and/or α -tocopherol levels and the incidence of cholestasis ([Burrin, et al. 2014](#), [Clayton, et al. 1998](#), [Ng, et al. 2015](#)), to address specific concerns communicated by the FDA given published experimental data ([Carter, et al. 2007](#), [El Kasmi, et al. 2013](#)).

Per the request of the FDA, length of stay in hospital, the number of independent bloodstream infections and mortality (as part of serious adverse event [SAE] analyses) will be evaluated as well.

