7 STATISTICAL CONSIDERATIONS AND DEFINITIONS

All data will be evaluated descriptively and in an exploratory way. Point estimates of differences between treatment groups and corresponding two-sided 95%-confidence intervals will be presented for the primary and key secondary efficacy endpoints. Statistical hypotheses will not be tested and p-values will not be reported.

The analysis of the primary and secondary efficacy endpoints will be performed using both the ITT analysis set and the per protocol set. The analysis of the secondary safety endpoints will be performed using the safety set.

Descriptive statistics will be displayed to provide an overview of the efficacy and safety results by treatment group, stratum and overall. For categorical parameters, these will consist of the number and percentage of patients in each category. The denominator for percentages will be based on the number of patients in the corresponding analysis set, missing will be displayed as a category. For continuous parameters, descriptive statistics will include number of patients with number of non-missing values, mean, standard deviation, median, minimum, and maximum.

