7.1 Changes in the Conduct of the Trial or Planned Analysis

The study was terminated early after the interim analysis and consultancy with the FDA. Changes in statistical analysis are described in this document and the Study Protocol Version 3.0.

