8.12.2 Other Secondary Safety Variables

For each patient, the ratio of the number of independent bloodstream infections and the number of days on study medication will be computed. The ratio, as well as the number and incidence of patients with at least one bloodstream infection will be summarized descriptively by underlying disease group, treatment arm and study phase. A data listing of number of bloodstream infections and number of days on study medication will be included.

The number and incidence of patients who complete PN treatment without lipid minimization, as well as the cumulative number of days of PN administration without lipid minimization will be summarized descriptively statistics by underlying disease, treatment arm and study phase. A corresponding data listing will be included.

The number of patients who need to be withdrawn from the study due to elevated conjugated bilirubin levels will be summarized with descriptive statistics by underlying disease, treatment arm and study phase.

Statistical Analysis Plan

FK Study Identifier: SMOF-018-CP3

8.12.3 Area under the curve of conjugated bilirubin for time period in which levels are > 1.5 mg/dL

The area under the curve (AUC_{>1.5}) is defined as the area between conjugated bilirubin concentrations > 1.5 mg/dL and the horizontal line at 1.5 mg/dL, restricted by the time point of study withdrawal, if applicable. The AUC_{>1.5} will be calculated using the Riemann method¹⁰, which is the same as the trapezoidal rule. An AUC value will only be used if there was no more than one conjugated bilirubin value missing. Descriptive summary statistics by treatment group and study phase and a detailed data listing will be presented.

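### SAP 8.12 gives only per-arm summaries for bloodstream infections, bilirubin withdrawals, deaths and serious TEAEs; between-arm estimates with 95% CIs should be added

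*Protocol*

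**What the plan says.** **Protocol.** Section 5.2 records that, at the FDA's request, "length of stay in hospital, the number of independent bloodstream infections and mortality (as part of serious adverse event [SAE] analyses) will be evaluated". Section 8.2.7 covers secondary measures for both efficacy and safety. After naming the between-group tests it says: "The corresponding effect size measures and confidence intervals will be presented in addition". The next paragraph deals with a stop after the interim because the sample size needed is not feasible. In that case "the analyses of secondary outcome measures will be performed only with descriptive statistics and the statistical tests planned above will be dropped". For adverse events the same section plans: "The number, intensity, relation to study medication and action taken will be described by frequency tables".

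**SAP.** Section 7.1 states: "The study was terminated early after the interim analysis and consultancy with the FDA". It gives no reason for the termination. Sections 4.5 and 7 make the whole analysis descriptive and exploratory, without hypothesis tests or p-values. They still provide point estimates of treatment differences, and two-sided 95% "confidence intervals will be presented for the primary and key secondary efficacy endpoints". Section 8.12 calls all secondary safety analyses descriptive. Within it:

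- 8.12.1.1 (time to discharge) and 8.12.1.2 (time to confirmed conjugated bilirubin > 2 mg/dL) each report a Fine and Gray hazard ratio with 95% CI.
- 8.12.2 computes infections per day on study medication for each infant. This ratio, "as well as the number and incidence of patients with at least one bloodstream infection will be summarized descriptively". Withdrawals for elevated conjugated bilirubin are handled in the same way.
- 8.12.4 reports serious and fatal TEAEs as patient counts, percentages and event counts by arm.

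**The concern.** The primary objective in SAP 3.1 is a comparison of safety. The FDA named three further outcomes, and the SAP attaches an estimate and interval to one of them. For infections and deaths the reader will see two percentages side by side and no measure of how far apart the true risks could be. In arms of this size, similar percentages are compatible with a substantial harm or a substantial benefit, and per-arm tables do not show that. The SAP does not explain why length of stay and time to bilirubin elevation are treated differently from infections, withdrawals, deaths and serious TEAEs.

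**Working it through.** No figure in the plan is in dispute, so the main check is a comparison of the texts.

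| Outcome | Status in the protocol | Requested by the FDA (5.2) | Between-arm estimate with 95% CI in the SAP |
|---|---|---|---|
| Confirmed conjugated bilirubin > 2 mg/dL by day 28 | Primary | – | Mantel-Haenszel relative risk (8.10) |
| Length of stay | Secondary safety | Yes | Hazard ratio (8.12.1.1) |
| Time to conjugated bilirubin > 2 mg/dL | Secondary safety | No | Hazard ratio (8.12.1.2) |
| Bloodstream infections (per day on drug; infants with at least one) | Secondary safety | Yes | None (8.12.2) |
| Withdrawal for elevated conjugated bilirubin | Secondary safety | No | None (8.12.2) |
| Death | Not listed separately; part of SAE analyses | Yes | None (8.12.4) |
| Serious TEAEs | Within AE data; frequency tables | Not as such | None (8.12.4) |

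Two things follow.

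1. The SAP does not regard an estimate with an interval as incompatible with a descriptive analysis. Sections 4.5 and 7 pair the two directly, and 8.12 calls the safety analyses descriptive while 8.12.1.1 and 8.12.1.2 report hazard ratios with intervals. The word descriptive therefore does not explain the four outcomes without an estimate.
2. For the two infection measures and for bilirubin withdrawal, the effect-size sentence in Protocol 8.2.7 applies on its face, because they are listed secondary outcomes. For deaths and serious TEAEs it does not clearly apply, because adverse events were assigned to frequency tables.

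**Illustration of the uncertainty.** The documents give no infection or death rates, so the counts below are assumptions. SAP 8.8 reports 152 randomized patients at the interim. With 1:1 allocation I assume 152 / 2 = 76 per arm.

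For *a* and *b* events among *n* per arm, the standard error of the log risk ratio is SE = √(1/a − 1/n + 1/b − 1/n), and the 95% limits are RR × exp(±1.96 × SE).

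- 15 vs 15 infants with infection (19.7% each): SE = √(2 × (1/15 − 1/76)) = 0.327, so RR 1.0, CI 0.53 to 1.90. For the risk difference, 1.96 × √(2 × 0.197 × 0.803 / 76) = 0.127, i.e. ±12.7 percentage points.
- 4 vs 4 deaths: SE = √(2 × (1/4 − 1/76)) = 0.688, so RR 1.0, CI 0.26 to 3.85; risk difference ±7.1 points.
- 8 vs 4 deaths: SE = √(1/8 + 1/4 − 2/76) = 0.590, so RR 2.0, CI 0.63 to 6.36.

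These intervals need no hypothesis test. They are unstratified and omit stage 2. SAP 8 says few patients were enrolled in stage 2, and 8.12 pools the stages, so the final intervals would use somewhat more data.

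**The case against.** A reader might infer that the SAP breaks a promise made in Protocol 8.2.7. The documents do not support that.

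- The early-stop paragraph confines the secondary analyses to descriptive statistics. The effect sizes were introduced as an addition to the tests, so one natural reading is that they go when the tests go. The paragraph names only the tests as dropped and is silent on effect sizes and intervals, so the point is ambiguous.
- The paragraph applies to a stop for infeasible sample size. The SAP gives no reason for termination, so it cannot be confirmed that the paragraph governs. The SAP's description of the analysis does resemble the protocol's wording for that case.
- Protocol 8.2.3 lets the SAP change statistical methods without an amendment if the change is documented. Protocol 8.2.7 also foresees competing-risk models in some cases, which is what the two safety hazard ratios are.
- Mortality was placed within the SAE analyses and adverse events in frequency tables. The SAP delivers those tables, and also shows death counts in the competing-risk summaries.

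A reader might also infer that intervals survive only for the primary and efficacy endpoints. That is wrong, because two safety endpoints keep one, including length of stay.

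All of this stands, and it removes any charge of non-compliance. It is also fair that the illustrative counts are hypothetical and that a crude interval for a binary outcome can be worked out from the published counts. That interval would be unstratified, however. The infection rate ratio could not be obtained from a summary of per-infant ratios; it would need the patient listing. None of these points gives a reason for leaving the estimates out.

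**Conclusion.** The point holds as a recommended improvement. The SAP compares the arms with an estimate and interval for the primary endpoint, key secondary efficacy endpoints and two safety endpoints. It gives per-arm summaries only for bloodstream infections, withdrawal for elevated conjugated bilirubin, deaths and serious TEAEs. One of the three FDA-requested outcomes receives a comparative estimate.

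The case rests on the comparative-safety objective, the FDA request and the SAP's own practice. It does not rest on a broken protocol commitment. Under the assumed counts with 76 per arm, equal observed percentages would be compatible with nearly a doubling or halving of infection risk (0.53 to 1.90), or with close to a fourfold difference in deaths in either direction (0.26 to 3.85). These figures show the order of the uncertainty and predict nothing about the trial's results.

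**What to change.** In SAP 8.12.2 and 8.12.4 add the following, on the safety set, with two-sided 95% CIs and no p-values:

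- A Mantel-Haenszel risk ratio and risk difference, stratified by NEC / No NEC, for at least one bloodstream infection, withdrawal for elevated conjugated bilirubin, death and any serious TEAE. Specify in advance an unstratified or exact interval where a stratum has no events, which is a real possibility for deaths.
- A between-arm rate ratio for independent bloodstream infections per day on study medication. The FDA asked for the number of infections, and a yes/no outcome alone does not answer that.

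Extend the sentence in SAP 4.5 and 7 to name these outcomes. If the sponsor prefers not to add them, the SAP should say why they are treated differently from length of stay.

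The cost is a few lines in tables already planned (14.3.7.3, 14.3.7.4, 14.3.9.1, 14.3.2.1 and 14.3.2.5). The stratified relative risk is already specified for the primary endpoint, and no new data are needed. The drawback is more unadjusted exploratory intervals, a position SAP 7.8 already accepts.
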